## 2.2.1 Modification of Standard Arm

The protocol was initially conceived as a comparison between six times per week nocturnal home hemodialysis and conventional three times per week in-center hemodialysis. This design had the advantage that the in-center hemodialysis control arm represented the current standard hemodialysis therapy, but also had the disadvantage that the effect of the duration or intensity of the dialysis treatment (6 times per week for six to seven hours overnight vs. 3 times per week for about 2.5 to 4.5 hours) was confounded with the location where the hemodialysis occurred (at home vs. incenter). Thus, using the original protocol design, it would not have been possible to distinguish between the effects of dialysis intensity versus dialysis location.

Several months after initiating enrollment, the Steering Committee determined that it would not be possible, using the original study design, to randomize an adequate number of patients to achieve the necessary sample size for adequate statistical power. Patients were reluctant to consider an intervention where there was only a 50% chance that they would be randomized to home hemodialysis therapy. Therefore, in accordance with the philosophy of the trial's Vanguard study design (see Section 4), the Steering Committee elected to change the location of dialysis in the

control arm from in-center hemodialysis to home hemodialysis. All other aspects of dialysis care in the control arm, including the frequency and dose of dialysis delivered, are unchanged form the original protocol (V 2.1). Once the revised protocol was approved by the Clinical Center's local IRB:

- 1) All new patients not previously randomized into the FHN study under version 2.1 will be randomly assigned to either six times per week nocturnal home hemodialysis or to three times per week conventional home hemodialysis.
- 2) Patients who consented to the original version (2.1) of the protocol and were already randomized to the home nocturnal arm prior to approval of the revised (V 3.0) protocol will remain with their assigned treatment group and original protocol, but will be asked to sign a new consent form to indicate that the design of the trial has changed for new patients.

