### 8.2 Purpose

If nocturnal home hemodialysis proves to be effective in improving health outcomes, it will be important to understand:

- a) The changes in dialysis center costs to provide this mode of hemodialysis,
- b) The changes in overall health care costs to insurers (principally CMS) of patients using this mode of hemodialysis,
- c) The cost-effectiveness of the intervention (change in insurer costs per change in quality adjusted life-years)
- d) Costs per month for in-center hemodialysis (three times per week) obtained from the Daily Trial will be used to compare the monthly costs of nocturnal home hemodialysis with 3 times per week in-center hemodialysis.

The purpose of the economic analysis in this trial is to provide answers to these questions.

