- f) Objective 3 Cost-Effectiveness: The impact of randomization to nocturnal hemodialysis (compared with standard 3 times weekly home hemodialysis) on life expectancy will be determined directly from survival of patients in the two arms of this trial. Utility (quality of life) will be determined from the Health Utilities Index. The impact of assigned treatment on quality adjusted life years will be calculated from the measures. If as hypothesized, nocturnal hemodialysis is a "dominant" strategy, improving survival/health utility and lowering costs, differences in survival, utility, dialysis costs, and total CMS costs will be presented in a cost-consequences framework. If, conversely, survival/health utility is improved, but total CMS costs are increased, we will calculate the incremental cost-effectiveness ratio (cost per qualityadjusted-life-year), to permit comparison with other possible ways for CMS to spend its health care dollar.
- g) **Objective 4 Comparison of nocturnal with short daily hemodialysis:** While not a primary purpose of this randomized trial, there will be interest in comparing the outcomes of overnight nightly home hemodialysis with the outcomes of short daily incenter dialysis being studied in the companion trial performed by this consortium. These results will not be directly comparable as the patient groups from which patients will be randomized are different. However the degree of difference (or conversely, of

comparability) may be estimated by comparison of the outcomes in the standard arm (conventional home hemodialysis three times weekly) in this trial and in the companion trial. We shall make such comparisons.

- h) Power: We acknowledge that the power for some of the above proposed analyses is likely to be poor. Specifically, formal power analyses have suggested that there will be low power to detect differences in patient survival and the rate of hospitalizations. The latter will likely be a major component of the total CMS costs of management of a dialysis patient. Therefore a major focus of this economic analysis will be the sensitivity analysis to determine robustness of our analyses.

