# 9.11 Statistical Power

Estimates of parameters for determination of study power were obtained primarily based on information from the HEMO Study database, with downward adjustments in mortality and hospitalization rates to account for the expectation of lower comorbidity among patients eligible for nocturnal dialysis. During the first year of follow-up in the HEMO Study, the mortality rate was 12%/year, the transplant rate was 4%/year, the rate of all non-access hospitalizations was 1.19 per year, and approximately 80% of patients remained in active follow-up at the 12 month assessment. To assure the power calculations are conservative, we have projected that mortality and hospitalization rates will be 40% lower in the control group of this trial than in the HEMO Study, and that transplantation rates will be slightly higher (6% per year instead of 4%), reflecting the expectation of a younger average age and inclusion of more incident patients. Data from the HEMO Study was also used to estimate the standard deviation of the change in the PHC, average serum albumin, average serum phosphorus, average pre-dialysis systolic blood pressure after controlling for the baseline value of outcome and pre-specified covariates. The standard deviation estimate of 24 g for the change in LV mass was estimated from the standard deviation of the change in LV mass by MRI obtained in 153 patients over 9 months by Pitt et al (2003).

The minimum detectable effect sizes for the co-primary PHC/Mortality and LV mass/Mortality composite endpoints of were estimated under the following assumptions: a) the target sample size of 90 randomized patients is achieved, b) exponentially distributed survival, with a 7%/yr mortality rate in the control group, c) exponentially distributed transplantation, with a 6%/yr transplantation rate in both treatment groups, d) measurements at 12 months of the PHC and LV mass outcomes will be obtained in 80% of randomized patients, e) normally distributed changes in the PHC and LV mass in those patients with 12-month measurements, with standard deviations (without covariate adjustment) of 9.12 PHC units and 24.0 g, respectively, f) utilization of the log rank test as described in Section 9.3, without covariate adjustment, and g) use of Hochberg's procedure to maintain an overall Type I error rate of  $\leq 5\%$ .

FHN Nocturnal Protocol Version 3.3: October 15, 2008

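### Economic Objective 4 reads the difference between the two trials' standard arms as a gauge of patient comparability, but one arm is now mostly at home and the other in-center, so the contrast is patient mix plus location

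*Protocol*

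**What the plan says.** Objective 4 in Section 8.4 g wants to compare nocturnal home dialysis with "short daily incenter dialysis being studied in the companion trial performed by this consortium". It warns that the two sets of results are not directly comparable, and the one reason it gives is that "the patient groups from which patients will be randomized are different". It then suggests that how different, or how comparable, they are can be judged through a "comparison of the outcomes in the standard arm (conventional home hemodialysis three times weekly) in this trial and in the companion trial", and it commits to making such comparisons.

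Three other places fix the setting of the two standard arms:

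- Section 2.2.1 records that the Steering Committee moved the "control arm from in-center hemodialysis to home hemodialysis". It explains that under the first design "it would not have been possible to distinguish between the effects of dialysis intensity versus dialysis location".
- Section 8.2 d relies on "Costs per month for in-center hemodialysis (three times per week) obtained from the Daily Trial", which places the companion trial's three-times-weekly dialysis in-center. The recruitment text in Section 4.1 also describes the companion trial as an in-center one.
- Section 9.4 keeps patients who were randomized to in-center dialysis before the change in this trial's standard arm, and expects more than half of them to transfer to home. Section 2.2.1 calls the patients randomized before the change a small fraction.

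**The concern.** Comparing control arms across two trials shows how far the patients differ only if both control arms receive the same care in the same setting. That would have been so while both controls were in-center three times a week. The label in 8.4 g was updated to home dialysis, but the reasoning around it was not: the paragraph still names patient groups as the only source of non-comparability.

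What is at stake is the reading of a cross-trial economic comparison. An effect of home care on outcomes could be taken for a difference between patients. If location and patient mix pulled in opposite directions, the standard arms could look alike and two different populations could be declared comparable. Section 8.4 h already admits low power for survival and hospitalization, so a null contrast would be easy to over-read.

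**Working it through.** Objective 4 states no figure, so there is nothing to reproduce. The question is what the contrast can identify.

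**Notation**, on an additive scale for any one outcome:

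- P: difference due to patient mix, this trial minus the companion trial.
- L: effect of home versus in-center dialysis.
- R: effect of the nocturnal regimen versus the short daily regimen.
- h: share of this trial's standard-arm follow-up spent at home. It is close to 1 if the patients randomized before the change are few, as Section 2.2.1 expects. The protocol gives no count.

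**Step 1. The standard-arm contrast.** Both arms are dialyzed three times a week, so regimen cancels:

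standard arm here − standard arm in companion trial = P + hL

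This is one observed quantity with two unknown parts. It equals P only if hL = 0, that is, only if location has no effect on the outcome. The protocol does not state that assumption, and Section 2.2.1 treats location as an effect to be separated from intensity. If P = −hL, the contrast is zero although the patients differ.

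**Step 2. The contrast Objective 4 is after.** Nocturnal dialysis is at home and short daily dialysis is in-center:

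nocturnal − short daily = R + P + L

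**Step 3. Comparison through each trial's randomized difference.**

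(nocturnal − its control) − (short daily − its control)
= (nocturnal − short daily) − (difference between the standard arms)
= (R + P + L) − (P + hL)
= R + (1 − h)L

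With h near 1 this is close to R, provided that effects add and that each regimen's effect does not depend on the patient group or the setting.

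So the standard-arm contrast is a sensible term to subtract, because it carries the background difference between the trials in population and setting together. It does not isolate the population part, which is what 8.4 g takes it to show.

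**Step 4. What could isolate the population part.** Under Sections 2.7 and 2.8, baseline data are collected before randomization and patients are dialyzed three times a week during training. The Vanguard benchmarks in Section 4.1 place the start of home dialysis after the post-randomization training. Baseline values in this trial therefore largely precede any effect of home care. They include the comorbidity index (Section 2.7) and the Health Utilities Index (Table 9 A).

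**The case against.** The strongest reply is that the location gap between the standard arms also separates the two intervention arms. Steps 2 and 3 bear this out: the standard-arm difference estimates the whole background gap, and it is exactly the term removed when each trial's randomized difference is used. For that purpose the move to a home control arguably helped. With an in-center control here, the contrast would have captured P alone and left L in the nocturnal-versus-daily comparison. This part stands. A reader might infer that the standard-arm contrast is worthless and should be dropped; the documents do not support that.

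It can also be said that a degree of difference need not mean patient mix alone. But 8.4 g gives patient groups as its only reason and does not mention location, so the natural reading is the one that fails. Taking the parenthetical label to describe both trials' standard arms does not help, because it would contradict 8.2 d.

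Two further inferences are tempting and do not hold:

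- **That Section 8.2 d has the same fault.** There the plan says "Costs per month for in-center hemodialysis (three times per week) obtained from the Daily Trial will be used to compare" in-center with nocturnal home dialysis, so the setting is part of the intended cost contrast and is not a confounder. Section 8.4 d computes monthly dialysis cost as a cost per session times the number of sessions. The center's session cost is built mainly from staff time, price lists and overhead (Table 10), which should depend little on how ill the patients are.
- **That Section 9.11 sizes the problem.** It projects that "mortality and hospitalization rates will be 40% lower in the control group of this trial than in the HEMO Study". This is a planning value, chosen to keep the power calculation conservative and attributed to lower comorbidity. It describes patient mix relative to another study, not the effect of location, and nothing in the protocol says that the companion trial's controls resemble that study's patients.

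Finally, Objective 4 is described as not a primary purpose, is worded tentatively, and has no test or decision attached. That limits the priority but does not repair the reasoning.

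**Conclusion.** The point holds in a limited form. Section 8.4 g commits to a contrast that cannot identify what it is said to estimate: it gives patient mix plus location, and reading it as patient comparability assumes that location has no effect. The size of the resulting error cannot be derived, because the protocol has no figure for home versus in-center dialysis on any outcome; its direction is also open. The patients randomized in-center before the change dilute the location part slightly and do not remove it.

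The conclusion rests on the companion trial's standard arm being in-center. That is taken from Sections 4.1, 8.2 d and 8.4 g, since the companion protocol is not at hand. No primary, main secondary or safety analysis is affected. Priority: minor.

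**What to change.** Reword Section 8.4 g in three respects:

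1. Gauge patient comparability by comparing the two trials on baseline characteristics and on outcome values measured before randomization, on three-times-weekly dialysis, as far as the companion trial collects the same items.
2. Compare nocturnal with short daily dialysis through each trial's own randomized treatment-minus-control difference, and state that the two control arms differ in setting.
3. Keep the standard-arm outcome contrast, labelled as a measure of the combined population-plus-setting difference and not of patient comparability.

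Section 8.2 d needs no change on this account. In this trial the baseline data are already planned; whether the companion trial holds matching items has to be confirmed. The cost is a few sentences of text and a more cautious cross-trial statement.

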### 9. Statistical Analyses

### 9.1 General Methods for Descriptive Summaries and Baseline Comparisons

Quantitative variables will be summarized with standard descriptive statistics and represented graphically with displays such as box plots, smooth density function estimates [Silverman, 1986] and histograms, and categorical variables will be described by frequency tables and standard graphical displays. Inferential analyses for quantitative variables will be performed using 2-group t-tests and, when appropriate, linear models such as analysis of variance and regression. Highly skewed variables may be transformed prior to inferential comparisons, or nonparametric methods employed. Categorical variables will be analyzed with 2-sample comparisons of proportions, logistic regression, general multinomial response models, and multinomial logistic models for ordered categorical outcomes [Agresti, 2002].

#### 9.2 Analyses of Recruitment Process

Descriptive summaries of clinical and demographic characteristics will be obtained for each of the stages of the recruitment process. The characteristics of each stage will be compared to each other and to the USRDS to address the representativeness of the FHN participants. Reasons for exclusion or dropout during baseline will be tabulated.

#### 9.4 Main Secondary Outcomes

As described in Section 9.3, the PHC/Mortality and LV mass/Mortality composites are the coprimary endpoints for evaluation of patient benefit in the trial. In addition, as described in Section 5.1.2, main secondary outcomes have also been designated for each of six specific and conceptually distinct physiological or quality of life-related outcome domains. These include: i) change over 12 months in the PHC; and, ii) change over 12 months in LV mass (without the mortality components), which represent the main secondary outcomes for evaluation of the physical function and cardiac structure and function domains, respectively. The remaining outcome domains and associated main secondary outcomes are iii) depression/disease burden (change over 12 months in Beck Depression Inventory), iv) nutrition (change over 12 months in serum albumin), v) cognitive function (change over 12 months in the Trails B), and vi) mineral metabolism (change over 12 months in average predialysis phosphorus). The primary evaluation of the effects of the treatment interventions on each of these seven outcome domains will be based on the designated main secondary endpoints. Analyses of other outcomes within each domain will be regarded as exploratory. Hypertension and anemia are also stipulated as main outcome domains, but are not conducive to the designation of a single main endpoint.

As described in Section 9.3, the PHC/Mortality and LV mass/Mortality composites are the coprimary endpoints for evaluation of patient benefit in the trial. In addition, as described in Section 5.1.2, main secondary outcomes have also been designated for each of seven specific and conceptually distinct physiological or quality of life-related outcome domains. These include: i) change over 12 months in the PHC; and, ii) change over 12 months in LV mass (without the mortality components), which represent the main secondary outcomes for evaluation of the physical function and cardiac structure and function domains, respectively. The remaining outcome domains and associated main secondary outcomes are iii) depression/disease burden (change over 12 months in Beck Depression Inventory), iv) nutrition (change over 12 months in serum albumin), v) cognitive function (change over 12 months in the Trails B), vi) mineral metabolism (change over 12 months in average pre-dialysis phosphorus), and vii) clinical events (rate of non-access hospitalizations or death). The primary evaluation of the effects of the treatment interventions on each of these seven outcome domains will be based on the designated main secondary endpoints. Analyses of other outcomes within each domain will be regarded as exploratory. Hypertension and anemia are also stipulated as main outcome domains, but are not conducive to the designation of a single main endpoint.

Two-sided tests will be used when testing the effects of the interventions on both the primary and secondary endpoints. The primary and main secondary analyses will be conducted by intention-to-treat in the sense that all patients analyzed according to their randomized assignment, irrespective of whether they adhered to the interventions. As noted above, however, follow-up will be censored at the time of renal transplantation. The analyses of the main secondary endpoints will be tested at the 0.05 level, without formal adjustment for multiple comparisons. However, nominally significant effects on individual secondary outcomes will be interpreted as consistent with Type I errors unless accompanied by significant effects of the interventions on the primary outcomes and a consistent pattern of treatment effects across multiple secondary outcomes.

The intention-to-treat analyses will incorporate all randomized patients, including patients randomized prior to the date at which the standard three times per week intervention was modified from in-center hemodialysis to home hemodialysis. Patients assigned to in-center three times per week therapy prior to the modification will be combined with patients assigned to standard home hemodialysis three times per week therapy after the implementation of the modification. The Steering Committee estimates that more than 50% of the patients initially assigned to standard in-center therapy will elect to transfer to home therapy. If the projected total sample size of 125 randomized patients in the standard three times per week is attained, the total patient years of follow-up on in-center therapy for the few patients randomized to the three times per week arm prior to the implementation of this modification is thus expected to comprise a small proportion of the total patient years of follow-up in this arm.

### 9.5 General Analytic Strategy for Quantitative Outcomes

The following analytic strategy will be employed for quantitative outcomes, including each of the main secondary outcomes with the exception of the rate of non-access hospitalization or death. The main analysis for each outcome will evaluate the treatment effect on the change from baseline to 12 months. For outcomes evaluated monthly (serum albumin and pre-dialysis phosphorus) the 12 month value will be averaged over the Months 10, 11, and 12 assessments for increased statistical power. For each outcome with multiple follow-up assessments (including the PHC, serum albumin, Beck Depression Inventory, Trailmaking Test B, and pre-dialysis phosphorus), an additional analysis will be conducted to evaluate the change from baseline to Month 4, where the Month 4 value is taken as the average value over months 3, 4, and 5 for serum albumin and pre-dialysis phosphorus. The analysis of change to 4 months will evaluate short term effects, while the analysis of change to 12 months will evaluate longer-term effects. The 4-month comparison is also intended to evaluate treatment effects prior to significant attrition. The "basic model" to be used for quantitative outcomes is:

$$\Delta \mathbf{Y}_{t} = \beta_{0t} + \beta_{1t} \operatorname{Trt} + \beta_{2t} \mathbf{Y}_{0} + \Sigma \gamma_{it} \mathbf{S}_{i} + \Sigma \delta_{it} \mathbf{F}_{i} + \varepsilon_{t}, \quad (\text{Basic Model})$$

where  $\Delta Y_t$  denotes the change in the response variable from baseline to time t, Trt is an indicator variable for the daily treatment intervention,  $Y_0$  is the baseline value of the response variable, the  $S_i$  are indicator variables for the Clinical Centers, the  $F_i$  are the following six pre-specified baseline covariates (age, race, years of dialysis, diabetic status, baseline serum albumin, and

FHN Nocturnal Protocol Version 3.3: October 15, 2008

baseline GFR), and the  $\varepsilon_t$  are random residuals at t = 4 and 12 months. The primary focus of the model will be to estimate the treatment effect  $\beta_{1t}$  as accurately as possible; the remaining terms are included to reduce residual variability and reduce bias from missing data. The model will be fit by restricted maximum likelihood [Harville, 1977] assuming an approximate normal distribution and with an unstructured covariance matrix for the residuals at the two time points. The change in the LV mass from baseline to its single follow-up assessment at 12 months will be analyzed by restricting the basic model to one time point, which simplifies to traditional analysis of covariance.

The target sample size of 90 patients is sufficient that inferences for the fixed effect terms in these analyses will remain valid with moderate departures from normality [Verbeke, 1997]. However, standard diagnostics will be performed and simulations conducted to address this issue, and modifications to the model will be made if necessary. In addition to evaluating the effects of the treatment interventions on LV mass, in grams, the effects of the interventions on the percentage change in LV mass will also be considered in secondary analyses.

